## 1 PROTOCOL SYNOPSIS

**Title** A Randomized, Double-Blind, Placebo-Controlled Study of COR388 HCl in Subjects with Alzheimer's Disease

**Objectives** The objectives of the study are to:

- Assess the efficacy of 2 dose levels of COR388 HCl in Alzheimer's disease (AD) subjects; and
- Assess the safety and tolerability of 2 dose levels of COR388 HCl in AD subjects.

**Study Phase** Phase 2/3

**Study Design** This is a randomized, double-blind, placebo-controlled study that will assess the efficacy, safety, and tolerability of 2 dose levels of COR388 HCl in subjects with probable AD dementia according to the National Institute on Aging-Alzheimer's Association (NIA-AA) criteria (McKhann 2011). The study will enroll approximately 573 generally healthy male and female subjects  $\geq 55$  and  $\leq 80$  years of age. Enrolled subjects must have a documented diagnosis of probable AD dementia with clinical evidence of progressive cognitive decline in the last year. Clinical decline will be defined as the evidence of progressive cognitive decline on sequential evaluations based on information from informants and/or cognitive testing in the context of either formal neuropsychological evaluation or standardized mental status examinations for probable AD dementia (McKhann 2011). The subject should not have other conditions or brain imaging abnormalities that can explain the symptoms of dementia. All subjects will have lumbar punctures (LPs) performed at baseline (Visit 2) and at end of treatment Week 48 (Visit 10) or early termination visit (ET). Cerebrospinal fluid (CSF) will be tested for measurement of bacterial DNA (*Pg*) using quantitative polymerase chain reaction (qPCR), biomarkers of AD, and gingipain activity. Saliva, and blood will be analyzed for biomarkers of AD and neuroinflammation, and for the presence of bacterial deoxyribonucleic acid (DNA) of *Porphyromonas gingivalis* (*P. gingivalis* [*Pg*]) using qPCR.

A subset of sites will be selected to monitor subjects for clinical evidence of periodontitis in addition to AD. An oral examination will be conducted by a study dentist/hygienist at these sites to assess for the presence of clinical evidence of periodontitis at screening, 24 and 48 weeks. Subgingival plaque (SGP) and buccal cell swabs will be collected at these sites and analyzed for measurements of biomarkers associated with *P. gingivalis* DNA, proteins, and inflammation.

Due to the nature of AD, subjects must identify a primary caregiver prior to enrollment in the study who will assist the subject with study participation. The primary caregiver must sign a caregiver informed consent.

The safety of study participants will be evaluated throughout the study by repeated physical examinations, vital signs, safety laboratory tests, 12-lead electrocardiograms (ECGs), Columbia-Suicide Severity Rating Scale (C-SSRS), magnetic resonance imaging (MRI), and assessments of treatment-emergent adverse events (TEAEs). Periodic safety reviews will be conducted during the study.

Following the Data Monitoring Committee (DMC) recommendation after the November 16, 2020 meeting, increased frequency of liver safety monitoring has been implemented, which increased the frequency of safety laboratory analyte collections (see [Table 1](#) and [Table 2](#), Schedule of Evaluations).

The study will consist of 3 periods: a screening period of up to 6 weeks, a treatment period of up to 48 weeks, and a safety follow-up period of 6 weeks. An interim analysis may be conducted to reassess the sample size and evaluate for efficacy after 24 weeks of treatment on key outcome measures.

### **Screening**

During the screening period, the eligibility of subjects will be confirmed according to the Schedule of Evaluations in this protocol. The Mini-Mental State Examination (MMSE) will be administered by a trained rater to assess the level of cognitive impairment. MMSE will be assessed as early in the screening period as possible. Subjects with MMSE score of 12-24, inclusive, will have the rest of their screening procedures performed or scheduled. Magnetic resonance imaging (MRI) of the brain will be performed in all subjects at screening, except subjects with an absolute contraindication for MRI, who can have a Computed Tomography (CT) scan of the brain instead. Screening procedures can be done on multiple days if needed, with more invasive procedures done after less invasive screening procedures are completed. A screen failure is any subject who signs the informed consent but does not qualify for the study or discontinues the study prior to randomization. A subject can be rescreened if the Principal Investigator thinks the subject may qualify for the study upon rescreening, and if the Medical Monitor agrees.

### **Treatment Period**

Subjects who meet all eligibility criteria will enter the treatment period and will be randomized 1:1:1 to receive 40 mg COR388 HCl, 80 mg COR388 HCl, or placebo twice a day. Randomization will be stratified by baseline MMSE (MMSE  $\geq 12$  and  $\leq 18$ , and MMSE  $\geq 19$  and  $\leq 24$ ) and Apolipoprotein E (ApoE4 positive either homozygous or heterozygous vs. all others) genotype to assure balanced distribution of mild and moderate AD and a balanced distribution of ApoE4 subjects, across treatment arms. Subjects will receive their assigned blinded study treatment orally twice a day for up to 48 weeks and will come back to the investigative site periodically for scheduled efficacy and safety evaluations. Blood samples for pharmacokinetics levels and biomarkers will be collected during selected visits. Baseline LP will be performed prior to the first dose of study drug, and follow-up LP will be done at the end of the treatment period. Subjects will continue to receive the study drug for 48 weeks, unless the Investigator determines that treatment of a given subject should

be stopped or interrupted for safety or tolerability reasons, the subject withdraws consent, or the Sponsor decides to stop the study.

***Safety Follow-up Period***

After completion of study treatment, subjects will continue to be monitored on the study for 6 weeks and will have a phone call to assess safety at Weeks 49 and 51 and will return for the Safety Follow-up Visit (Week 54).

For subjects with early termination, end of study procedures (Week 48) will be performed, and subjects will be encouraged to return to the clinic for the Safety Follow-up Visit after 6 weeks. Phone calls will be performed to assess safety at Week 1 and Week 3 after end of study procedures are performed.

***Open Label Extension***

The open label extension (OLE), as described below, was implemented in protocol versions 4.0 through 6.0. On 16 February 2021, the Sponsor terminated the OLE portion of the study following notification from the Food and Drug Administration (FDA) of a partial clinical hold. Per this notification, no new patients were enrolled into OLE, and all active participants were discontinued from study treatment with a requirement that a follow-up visit occur 4 weeks after the last dose of COR388.

***Open Label Extension Period***

Subjects who choose to participate in the OLE portion of the study and meet all eligibility criteria will begin the treatment period after completing the Week 48 Visit. Subjects will receive COR388 HCl 40 mg or 80 mg treatment orally twice a day for up to 48 weeks and will come back to the investigative site periodically for scheduled efficacy and safety evaluations. Subjects will continue to receive the study drug for 48 weeks, unless the Investigator determines that treatment of a given subject should be stopped or interrupted for safety or tolerability reasons, the subject withdraws consent, or the Sponsor decides to stop the study.

***Open Label Extension Safety Follow-up Period***

After completion of study treatment for the OLE, subjects will continue to be monitored on the study for 6 weeks and will have 2 phone calls to assess safety at Week 97 and Week 98 and will return for the Safety Follow-up Visit at Week 102.

For subjects with early termination, end of study procedures (Week 96) will be performed, and subjects will be encouraged to participate in the Safety Follow-up phone calls and return to the clinic for Safety Follow-up Visit.

**Study Population** The study will enroll approximately 573 generally healthy male and female subjects,  $\geq 55$  and  $\leq 80$  years of age, with mild to moderate probable AD dementia according to the NIA-AA criteria, who experienced clinical decline in the last year as defined in the study protocol.

**Criteria for Inclusion & Exclusion** Investigators should contact the Medical Monitor if they have questions about eligibility of specific subjects.

**Inclusion Criteria:**

Subjects will be eligible to participate in this study if they meet all of the following criteria:

1. Subject has provided full written informed consent prior to the performance of any protocol-specified procedure; or if unable to provide informed consent due to cognitive status, subject has provided assent and a legally authorized representative has provided full written informed consent on behalf of the subject.
2. Caregiver has provided full written informed consent, on a separate informed consent form (ICF), on his/her own behalf prior to the performance of any protocol-specified procedure.
3. Male and female subjects must be 55 years to 80 years of age, at the time of consent.
4. Subject has probable AD dementia according to the NIA-AA criteria ([McKhann 2011](#)) with clinical evidence of progressive cognitive decline in the last year. Clinical decline will be determined based on serial cognitive test scores, if available, or subject/caregiver report as documented by the Investigator.
5. Subject has an MMSE score between 12 and 24 inclusive at both screening and Visit 2 and a  $\leq 3$ -point difference between these visits.
6. Subject has a Modified Hachinski score  $\leq 4$  at screening.
7. Subject has brain MRI scan consistent with the diagnosis of AD performed during the screening period. Computed Tomography scan can be used only if the subject has an absolute contraindication for MRI.
8. Subject has a primary caregiver willing to accept responsibility for supervising the treatment (e.g., administering study drug), accompanying the study subject to clinic visits and assessing the condition of the subject throughout the study in accordance with all protocol requirements.
9. Subject is not likely to experience a change in living conditions (e.g., institutionalization, moving to a different city, etc.), or change in primary caregiver, during participation in the trial.
10. Subjects with background symptomatic therapy with acetylcholinesterase inhibitors, and/or memantine, are allowed as long as the dose has been stable for 90 days prior to screening and no changes are planned during the study.
11. Subjects who have occasional use of sedative agents are acceptable, but these agents should not be given within 48 hours prior to cognitive assessments.
12. Subjects who have background medications used for stable chronic illnesses that are not prohibited by the protocol are allowed. The dose of psychoactive drugs must be stable for 30 days prior to screening, and no changes must be planned during the study unless for safety reasons.
13. Subject has body mass index  $\leq 38$  kg/m^2 at Screening.
14. Subject must be able to ingest oral medications and can swallow the study drug without breaking or crushing.

15. Subject must be willing to undergo Apolipoprotein E genotype (ApoE) genetic testing (ApoE results may be disclosed after trial completion).
16. Subjects participating in the study must meet one of the following criteria:
  - a. Females: Surgically sterilized (e.g., hysterectomy, bilateral oophorectomy or tubal ligation) for at least 6 months or postmenopausal (postmenopausal females must have no menstrual bleeding for at least 1 year). If not postmenopausal, agree to use a highly effective method of contraception that can achieve a failure rate of less than 1% per year when used consistently and correctly, such as hormonal contraception or a double barrier method (e.g., intrauterine device plus condom or true abstinence defined as in line with the preferred and usual lifestyle of the subject. Periodic abstinence e.g. calendar, ovulation, symptothermal, post-ovulation methods are not acceptable. Declaration of abstinence for the duration of a trial, and withdrawal are not acceptable methods of contraception) from 30 days prior to dosing until 30 days after last dose and have negative human chorionic gonadotropin ( $\beta$ -hCG) test for pregnancy at screening.
  - b. Males who have not had a vasectomy must use appropriate contraception methods (barrier or true abstinence defined as in line with the preferred and usual lifestyle of the subject. Periodic abstinence e.g. calendar, ovulation, symptothermal, post-ovulation methods are not acceptable. Declaration of abstinence for the duration of a trial, and withdrawal are not acceptable methods of contraception) from 30 days prior to dosing until 90 days after last dose.

**Open Label Extension:** Subjects will be eligible to participate in the open label extension portion of the study if they meet inclusion criteria # 8, 9, 10, 11, 12, 14, and 16 above. Subjects with any change in their medical history that in the Investigator's opinion will increase the subject's risk of participating in the study or confounding study assessment should not continue in the open label extension portion of the study. The Investigator should contact the Sponsor with questions of eligibility for participation.

**NOTE:** Effective 16 February 2021, the OLE portion of the study was terminated by the Sponsor.

**Exclusion Criteria:**

Subjects will not be eligible to participate in this study if they meet any of the following exclusion criteria:

1. Subject has imaging consistent with other differential dementia diagnoses other than the diagnosis of AD. For example, any suggestion of vascular disease including multiple infarction involving large blood vessels or localized single infarction (angular gyrus, thalamus, anterior cerebral artery and posterior cerebral artery region), multiple lacunae of the basal nuclei or white matter or extensive lesions of the periventricular white matter or combination of several lesions are considered exclusionary.

Additionally, any single lacune in an area known to impact cognition such as the hippocampus will also be exclusionary. Finally, Probable CAA with/without supporting pathological evidence according to the modified Boston criteria, if in the opinion of the investigator this may be contributing to symptoms overlapping with those of AD or confound neuropsychological assessments, would be exclusionary. Importantly, should there be any evidence of neurologic symptoms between scanning and baseline visits, rescanning is necessary to ensure proper patient selection.

2. Subject has had an increase or restoration of cognition based on medical history.
3. Subjects who meet the following imaging exclusion criteria will not be included in this study:
  - a. Claustrophobia that will result in significant anxiety and difficulty lying still for brain imaging (MRI or CT scan).
  - b. Severe motor problems or chronic pain indication that prevents the subject from lying still for brain imaging.
4. Subject with history of cancer requiring systemic therapy in the last 5 years; except for localized cancer of the skin and in-situ cervical cancer successfully treated with surgical excision. Stable (for at least 90 days) prostate cancer is allowed.
5. Subject has a contraindication for LP, such as infected skin over the needle entry site, possible increased intracranial pressure, severe thrombocytopenia or coagulopathy, suspected spinal epidural abscess, or spinal structural abnormalities that would interfere with LP procedures.
6. Subject has evidence of clinically significant unstable cardiovascular, pulmonary, renal, hepatic, gastrointestinal, neurologic or metabolic disease within 6 months prior to Screening.
7. Subject has any of the following cardiovascular conditions:
  - a. Unstable angina, uncompensated and/or symptomatic congestive heart failure (Grade 2 or higher on the New York Heart Association scale) or myocardial infarction within 6 months.
  - b. Acute or poorly controlled blood pressure >180 mmHg systolic or >100 mmHg diastolic.
  - c. Current, or recent history of, any of the following that are clinically significant in the investigator's judgment: arrhythmia, hypotension, heart block (1st, 2nd or 3rd degree AV block), ANY bundle branch block, ventricular pacing, symptomatic ectopy, unstable arrhythmias including atrial fibrillation; stable atrial fibrillation is allowed.
  - d. History of prolonged QT or prolonged QT on screening ECG (QTcF  $\geq$ 480 msec).
  - e. History of prolonged PR interval or prolonged PR interval on screening ECG (PR >210 msec).

- f. History of prolonged QRS interval or prolonged QRS interval on screening ECG (QRS >120 msec).
  - g. Supraventricular or ventricular ectopy on the screening ECG or Brugada pattern on the ECG.
8. Subject with major stroke, uncontrolled seizure disorder, or other medical illnesses that in the Investigator's opinion will increase the subject's risk of participation in the study or confound study assessments.
9. Subject with history or current evidence of major neurological or psychiatric illness such as schizophrenia, bipolar disorder, Parkinson's Disease, etc. Subjects with major depressive disorder that may interfere with the patient's ability to perform the study and all assessments. NOTE: Mild depression or depressive mood arising in the context of AD are not criteria for exclusion. The use of anti-depressants or the use of anti-epileptic medication for non-seizure-related treatment is allowed if the dose has remained stable for at least 60 days prior to enrollment.
10. Subject with history of violent or aggressive behavior that requires medication to control.
11. Subjects with active suicidal thoughts (Type 4 or 5 on the C-SSRS) in the 6 months preceding screening or at baseline; or have a history of a suicide attempt in the previous 2 years, or more than 1 lifetime suicide attempt; or are at serious suicide risk in the Investigator's clinical judgment.
12. Subject with history of alcohol or drug use disorder within 12 months of screening as defined by the Diagnostic and Statistical Manual of Mental Disorders-5.
13. Subject with previous treatment with investigational vaccine therapy for AD.
14. Subject has participated in another Investigational New Drug (IND) research study involving small molecule drugs within 60 days or biological drugs within 90 days prior to the first dose of study drug or 5 half-lives of the investigational drug, whichever is longer.
15. Subject has a history of epilepsy or seizure disorder requiring ongoing treatment, or any seizure or loss of consciousness within 6 months prior to enrollment.
16. Subject has any of the following laboratory findings at screening:
  - a. Alanine aminotransferase >3 x upper limit of normal (ULN), aspartate aminotransferase >3 x ULN, or history of clinically significant liver disease in the Investigator's judgment.  
**NOTE:** Subjects with ALT or AST >2 x ULN at Visit 9/Week 40 will not be eligible to participate in OLE.  
**NOTE:** Effective 16 February 2021, the OLE portion of the study was terminated by the Sponsor.
  - b. Hemoglobin  $\leq$ 10 g/dl.

- c. International Normalized Ratio (INR) >1.5 or total bilirubin >1.5 x ULN (unless subject has evidence of Gilbert's disease).
  - d. Creatinine clearance (CL) of <45 ml/min.
  - e. Poorly controlled diabetes as defined by hemoglobin A1c (HbA1c) >8.
  - f. Positive blood screen for Human Immunodeficiency Virus (HIV 1 and 2), Hepatitis B surface antigen (HBsAg), or Hepatitis C virus antibodies (HCV-Ab) at Screening.
  - g. Positive urine screen for drugs of abuse that include opiates, cocaine, amphetamines, or barbiturates.
17. Subject has abnormal laboratory tests that suggest an alternate etiology for dementia, such as serum vitamin B12 deficiency, thyroid function abnormality, severe anemia, electrolyte abnormality, or positive syphilis serology. In these cases, the patient should be re-evaluated to determine if these potential causes of dementia have been addressed. Only if these causes have been ruled out as the cause of the dementia can the patient be enrolled.
18. Use of systemic (i.e., oral, intravenous, etc., but not topical) antibiotics in the last 60 days or history of recurrent infection that requires chronic or repeated courses of antibiotics.

**Open Label Extension:** Subjects will not be eligible to participate in open label extension portion of the study if they meet any of the following exclusion criteria # 1, 4, 6, 7, 8-12, 15, 16 a, b, c, d and e. Laboratory testing and ECG results from Visit 9 will be used to evaluate eligibility. Subjects with any change in their medical history that in the Investigator's opinion will increase the subject's risk of participating in the study or confounding study assessment should not continue in the open label extension portion of the study. The Investigator should contact the Sponsor with questions of eligibility for participation.

**NOTE:** Effective 16 February 2021, the OLE portion of the study was terminated by the Sponsor.

**Study Treatments** Eligible subjects will be randomized 1:1:1 to receive one of the following treatments:

- 80 mg COR388 HCl, twice daily (bid);
- 40 mg COR388 HCl, bid; or
- Placebo, bid

Open Label Extension: Subjects will receive 40 mg or 80 mg COR388 HCl, bid.

**NOTE:** Effective 16 February 2021, the OLE portion of the study was terminated by the Sponsor.

**Drug Supplies** The study drug will be provided in capsule form for oral administration. All capsules will be identical in appearance.

**Duration of Subject Participation** **Double-blind:** 48 weeks of treatment + up to 6 weeks for screening + 6 weeks Safety follow up for subjects who don't participate in open label extension  
**Open Label Extension:** 48 weeks of treatment + 6 weeks for Safety follow-up  
**NOTE:** Effective 16 February 2021, the OLE portion of the study was terminated by the Sponsor.  
**Total Duration of Participation:** up to 108 weeks

**Efficacy Evaluations**

The two co-primary endpoints are:

- Mean change in Alzheimer's Disease Assessment Scale-Cognitive Subscale 11 (ADAS-Cog 11) from baseline to the end of treatment period.
- Mean change in Alzheimer's Disease Cooperative Study Group-Activities of Daily Living (ADCS-ADL) from baseline to the end of treatment period.

Secondary endpoints in all subjects include:

- Change in Clinical Dementia Rating-Sum of Boxes (CDR-SB).
- Change in Mini-Mental State Examination (MMSE)
- Change in Neuropsychiatric Inventory (NPI)

Exploratory endpoints in all participating subjects include change from screening/baseline and/or Visit 2 to the end of treatment period in the following measures:

- 
- Blood-based biomarkers in serum and peripheral blood mononuclear cells (PBMCs); and
- Saliva biomarkers of *P. gingivalis* infection and inflammation.
- Cerebrospinal fluid:
  - CSF A $\beta$ 42, total Tau, and phosphorylated Tau;
  - Bacterial DNA in the CSF based on quantitative polymerase chain reaction (qPCR) and sequencing; and
  - CSF biomarkers.

Exploratory endpoints in subjects participating in sub-studies include change from screening/baseline to the end of treatment period in the following measures:

- Winterlight Speech Assessment (only in English speaking (primary language) subjects and only in the US and UK);
- Magnetic resonance imaging sub-study (subjects who have MRIs done in conjunction with the study):
  - Hippocampal volume; and
  - Cortical thickness.

- Clinical periodontitis sub-study (subjects enrolled at selected sites):
  - Pocket Depth (PD);
  - Clinical Attachment Level (CAL) at 6 sites per tooth (distobuccal [DB], buccal [B], mesiobuccal [MB], distolingual [DL], lingual [L], and mesiolingual [ML]);
  - The percentage of sites with Bleeding on Probing (BOP); and
  - Biomarkers of *P. gingivalis* infection and inflammation in subgingival plaque (SGP) and buccal cell swabs.

**Safety Endpoints** Safety endpoints include:

- The incidence and severity of TEAEs;
- Vital signs and physical examinations;
- Laboratory values;
- MRI scans;
- 12-lead ECGs; and
- C-SSRS.

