## **7.2 Study Treatment: Visit 2 (Day 0)**

Subjects who meet all of the eligibility criteria will be scheduled for Visit 2.

Note: To accommodate the logistics of performing the baseline LP procedure, a separate visit within 7 days prior to V2/Day 0 may be scheduled. At this visit,

baseline MMSE score will be verified, and the LP procedure will be performed. The remaining V2 assessments must be completed at Day 0, when the first dose of study drug will be administered.

The following evaluations will be performed at this visit in the following order or as close as possible when feasible:

1. MMSE;
2. Lumbar puncture to collect cerebrospinal fluid (CSF) may be conducted up to 7 days prior to other procedures listed below;
3. Inclusion/exclusion criteria to assess for continued eligibility.
4. ADAS-Cog 11;
5. Alzheimer's Disease Cooperative Study Group - Activities of Daily Living (ADCS-ADL);
6. CDR-SB;
7. Randomization;
8. Concomitant medications;
9. Symptom-based physical examination;
10. Vital signs;
11. Neuropsychiatric Inventory (NPI);
12. C-SSRS;
13. Urine drug screen;
14. Blood/urine sample collection:
  - a. Pharmacokinetics (PK): A pre-dose trough sample will be drawn immediately prior to the AM dose. The exact times of AM dosing and PK sample collections at the site will be documented.
  - b. Serum and whole blood (peripheral blood mononuclear cells [PBMCs]) for biomarkers; and
  - c. Safety laboratory tests;
15. Saliva collection;
16. Winterlight Speech Assessment (only in English speaking (primary language) subjects and only in the US and UK);
17. Adverse events;
18. Administer study drug at the site;
19. 12-lead ECG 1-1.5 hours post-dose;
20. Blood sample collection: Second PK blood draw 30 minutes to 4 hours post-dose; and
21. Dispense study drug.

A screen failure is any subject who signs the informed consent but does not qualify for the study or discontinues the study prior to randomization. A subject can be rescreened if the Principal Investigator thinks the subject may qualify for the study upon rescreening, and if the Medical Monitor agrees.

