### **7.7 Study Treatment: Visit 7 (Day 168 ± 3)**

Note: Please make every effort possible to have the visit scheduled in the morning so the AM dose can be taken in the morning. Ideally, daily doses should be taken 12 hours apart and no less than 6 hours apart.

The following evaluations will be performed at this visit in the following order or as close as possible when feasible:

1. ADAS-Cog 11;
2. MMSE;
3. ADCS-ADL;
4. CDR-SB;
5. NPI;
6. Winterlight Speech Assessment (only in English speaking (primary language subjects and only in the US and UK);
7. Concomitant medications;
8. Oral examination and collection of oral biomarker samples (SGP and buccal cell swabs) (only at selected sites);
9. Saliva collection;
10. Symptom-based physical examination;
11. Vital signs;

12. C-SSRS;
13. Blood/urine sample collection:
  - a. Safety laboratory tests;
  - b. PK - A pre-dose trough sample will be drawn and the subject will then take their dose of study drug on-site. The exact times of AM dosing and PK sample collections at the site will be documented.
  - c. Serum and whole blood (PBMCs) for biomarkers;
14. Adverse events;
15. 12-lead ECG before dosing drug (trough);
16. Administer study drug at the site;
17. 12-lead ECG 1-1.5 hours post-dose;
18. Blood sample collection: Second PK blood draw 2 hours  $\pm$  30 minutes post-dose; and
19. Dispense study drug.

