### **7.10 Study Treatment: Visit 10/Early Termination (Day 336 ± 8)**

Note: To accommodate the logistics of performing the LP procedure, it may be done up to 7 days prior to V10/Day 336. Please make every effort possible to have the visit scheduled in the morning so the AM dose can be taken in the morning. Ideally, daily doses should be taken 12 hours apart and no less than 6 hours apart.

The following evaluations will be performed at this visit or at Early Termination in the following order as close as possible when feasible:

1. Administer last dose of double-blind study drug at the site;
2. Blood/urine sample collection:
  - a. Safety laboratory tests;
  - b. PK - A single post-dose sample will be drawn from each subject while on-site at the clinic at 4 hours ± 30 minutes post-dose. The exact times of AM dosing and PK sample collections at the site will be documented.
  - c. Serum and whole blood (PBMCs) for biomarkers;
  - d. Pregnancy test (only if urine pregnancy test is positive);
3. Adverse events;
4. Oral examination and collection of oral biomarker samples (SGP and buccal cell swabs) at selected sites (will be completed within 8 days before Visit 10 [or Early Termination] when applicable).
5. 12-lead ECG 1-1.5 hours post-dose
6. MRI of the brain, only in subjects who had a screening MRI performed, and has to be done within 8 days prior to Visit 10. CT scans of the brain can be used instead of MRIs, only in subjects who have an absolute contraindication for MRI;
7. ADAS-Cog 11;
8. MMSE;
9. ADCS-ADL;
10. CDR-SB;
11. NPI;
12. Winterlight Speech Assessment (only in English speaking (primary language subjects and only in the US and UK);
13. Concomitant medications;
14. Symptom-based physical examination;
15. Saliva collection;

16. Weight;
  17. Vital signs;
  18. Lumbar puncture to collect CSF;
  19. Urine pregnancy test (women of child bearing potential only);
  20. C-SSRS;
  21. Informed consent will be obtained for subjects who agree to participate in the open label extension portion of the study; and
  22. Inclusion/exclusion will be evaluated to determine eligibility for subjects who want to participate in the open label extension portion of the study.  
Dispense OLE study drug – subjects who participate in OLE only. The subject should be instructed to take the first dose of COR388 in the morning of the next day.
- NOTE:** Effective 16 February 2021, the OLE portion of the study was terminated by the Sponsor.

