## 8.22 Cerebrospinal Fluid (CSF) Evaluations

The LP procedures, and medical care of the subject, will be administered as per clinical site standards including imaging prior to procedure, if applicable. Cerebrospinal fluid will be tested for measurement of bacterial DNA (*Pg*) using qPCR, biomarkers of AD, and gingipain activity. The details of sample collection and processing procedures will be provided in the Laboratory Manual. CSF samples will be sent to the central laboratory to be distributed to a specialty laboratory for biomarker analysis.

Assessments will be performed up to 7 days prior to study drug dosing at Baseline (Visit 2) and Visit 10 (or Early Termination).

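### Blood and saliva biomarkers are listed before the on-site dose at Weeks 0 and 24 but after it at Week 48, so the exploratory end-of-treatment change may carry an avoidable difference in drug level in the active arms only

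*Protocol*

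**What the plan says.** The Synopsis (Efficacy Evaluations) introduces the relevant endpoints thus: "Exploratory endpoints in all participating subjects include change from screening/baseline and/or Visit 2 to the end of treatment period in the following measures". The list that follows includes "Blood-based biomarkers in serum and peripheral blood mononuclear cells (PBMCs" and saliva biomarkers of *P. gingivalis* infection and inflammation. Section 4.1.2 repeats this. The end-of-treatment visit is Visit 10 (Week 48).

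The visit lists in Section 7 place the samples as follows:

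- **Visit 2 (7.2).** Item 14b is "Serum and whole blood (peripheral blood mononuclear cells [PBMCs]) for biomarkers; and"; the next item is "15. Saliva collection". Dosing comes later: "18. Administer study drug at the site".
- **Visit 7 (7.7).** Saliva is item 9 and biomarker blood item 13c. Dosing follows: "16. Administer study drug at the site". However, item 13b, on the PK trough sample, already has the subject taking the dose once that sample is drawn, one line before 13c.
- **Visit 10 (7.10).** Item 1 is "Administer last dose of double-blind study drug at the site". Biomarker blood is item 2c and saliva item 15. No pre-dose sample is listed.

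All three lists are qualified: the order is to be kept as closely as feasible.

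For CSF, Section 8.22 says "Assessments will be performed up to 7 days prior to study drug dosing at Baseline (Visit 2) and Visit 10" (or early termination). Section 7.10 lists the lumbar puncture as item 18, after the dose, while its opening note and Table 1 footnote 6 allow it up to 7 days earlier.

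PK samples and on-site-dose ECGs have stated times relative to dose. The protocol gives none for serum, PBMC or saliva biomarkers.

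**The concern.** The exploratory change compares a Week 48 sample with a drug-free baseline. If the Week 48 sample is taken some hours after a dose, it reflects 48 weeks of treatment plus the most recent dose. Week 24 samples, taken before the dose, would carry only the trough level. The extra exposure occurs in the two active arms alone, so the comparison with placebo does not cancel it.

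At stake is the reading of the trial's own evidence on mechanism. If a marker responds within hours to drug concentration, part of its difference from placebo at Week 48 would be a short-lived post-dose effect rather than a sustained one. A collection time that is not recorded cannot be recovered later.

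**Working it through.** The plan gives no figure on this point to reproduce. The check has two parts.

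**1. Order of procedures (item numbers from 7.2, 7.7 and 7.10)**

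| Visit | Serum/PBMC | Saliva | On-site dose | Listed order |
|---|---|---|---|---|
| 2 (Week 0) | 14b | 15 | 18 | before dose |
| 7 (Week 24) | 13c | 9 | 16 | before dose (blood ambiguous because of 13b) |
| 10 (Week 48) | 2c | 15 | 1 | after dose |

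**2. Drug level at the sample relative to trough**

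Inputs: half-life 4.5-5.0 h at steady state in humans (Section 2); doses ideally 12 h apart (5.1); Tmax about 1-1.5 h (8.23); Visit 10 PK sample at 4 h ± 30 min (7.10, 8.21).

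*Simple decay.* C(t)/C(12 h) = 2^((12 − t)/t½).

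- t = 3.5 h, t½ = 4.5 h: 2^(8.5/4.5) = 3.70
- t = 4.5 h, t½ = 5.0 h: 2^(7.5/5.0) = 2.83
- t = 1.25 h, t½ = 4.5 h: 2^(10.75/4.5) = 5.24
- t = 1.25 h, t½ = 5.0 h: 2^(10.75/5.0) = 4.44

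Biomarker blood drawn with the 4-hour PK sample therefore sees about 2.8-3.7 times trough, and a draw around Tmax about 4.4-5.2 times.

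*Cross-check with absorption.* Assume a one-compartment oral model at steady state with 12-hour dosing: C(t) ∝ [ka/(ka − ke)] × [e^(−ke·t)/(1 − e^(−12ke)) − e^(−ka·t)/(1 − e^(−12ka))]. Here ke = ln 2/t½, and ka is solved to give the stated Tmax. Levels as a share of peak:

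| t½ (h) | Tmax (h) | trough | 1 h | 4 h | 4.5 h | 1 h ÷ trough | 4.5 h ÷ trough |
|---|---|---|---|---|---|---|---|
| 4.5 | 1.0 | 0.19 | 1.00 | 0.67 | 0.62 | 5.3 | 3.3 |
| 4.5 | 1.5 | 0.22 | 0.96 | 0.75 | 0.70 | 4.4 | 3.2 |
| 5.0 | 1.0 | 0.23 | 1.00 | 0.69 | 0.65 | 4.3 | 2.8 |
| 5.0 | 1.5 | 0.25 | 0.96 | 0.77 | 0.72 | 3.8 | 2.9 |

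Both methods give roughly 3-5 times trough between 1 and 4.5 h.

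*Where saliva falls.* At Visit 10 it is listed after the rating scales. From Section 8 their durations are ADAS-Cog 11 30 min, MMSE 20, ADCS-ADL 20-25, CDR-SB 45-60, NPI 15 and Winterlight up to 10 (some subjects only). The total is 130-160 min, or 2.2-2.7 h. If the scales start after the ECG at 1-1.5 h, saliva falls at about 3-4 h, within the same range.

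**The case against.** The case on the other side is substantial, and most of it limits the point.

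- **No acute response is shown.** Section 2 describes COR388 as an irreversible inhibitor, so its effect need not follow plasma level hour by hour. Blood and saliva are assigned mainly to bacterial DNA, AD markers and neuroinflammation; gingipain activity is named for CSF. Nothing shows any of these moving within hours of a dose. The ratios above are drug levels, not effects on an endpoint. This stands.
- **List position is not clock time.** The order holds only where feasible, and the Visit 10 list is plainly not chronological: the 4-hour PK sample precedes the 1-1.5 h ECG. Item 13b leaves the Week 24 blood draw uncertain. This stands, but it also means that a post-dose draw at Visit 10 is neither ruled out nor timed.
- **The Laboratory Manual may set times.** Sections 8.11, 8.19 and 8.22 refer to it, and it is not available here. It would still have to agree with the visit lists.
- **Some mitigation exists.** Dose time at Visit 10 is recorded, and saliva has an off-drug sample at Visit 11 (Week 54). Serum and PBMC do not.
- **Only exploratory endpoints are involved**, analysed without multiplicity adjustment (11.3.2.4).

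A reader might infer that Week 48 samples are taken near peak. That fits only an early draw: at 4 h the model gives 67-77% of peak. A reader might also infer that the Week 24 to Week 48 trend is uninterpretable, but no such trend analysis is stated. Finally, 8.22 and 7.10 might look like a serious conflict on CSF. The 7-day allowance largely resolves it, leaving one item's position to be tidied.

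**Conclusion.** The point holds as a low-severity improvement. As listed, serum, PBMC and saliva biomarkers move from before the on-site dose at Visit 2 (and, less clearly for blood, at Visit 7) to after it at the visit that defines the endpoint. If the order is followed, active-arm samples taken about 1-4.5 h after the dose see roughly 3-5 times trough, with no corresponding shift on placebo. This rests on the protocol's half-life and Tmax, a 12-hour interval, and the assumed decay or one-compartment model.

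Whether any endpoint is affected depends on an acute response to drug level that the protocol does not demonstrate. Confounding is therefore possible, not established, and its size for any marker cannot be given. Exposure may also vary within the active arms. Under Section 12.13, subjects who stop for drug-related safety reasons have the Visit 10/ET procedures only after the concern has stabilised or resolved, possibly well after their last dose. The co-primary endpoints and their analysis are not touched.

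**What to change.** 1. In 7.10, place serum/PBMC biomarker blood and saliva collection before the on-site dose. Keep the 4-hour PK sample after it. Section 8.21 already has subjects arrive at Visit 10 before taking their morning dose.
2. In 7.7, reword items 13b and 13c so that biomarker blood is clearly drawn before the dose.
3. Reconcile the position of the Visit 10 lumbar puncture in 7.10 with 8.22.
4. Record time since last dose for every biomarker sample, including CSF taken up to 7 days ahead of the visit and samples at early termination. Check that the Laboratory Manual agrees.

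The cost is a reordered list, one time field and at most one additional venipuncture at Visit 10, comparable to the pre- and post-dose draws already made at Visit 7. No dose or treatment rule changes.
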